We estimate a total sample size of 1080 children with SAM (360 per arm) and 1080 children with MAM (360 per arm) will provide at least 90% statistical power to demonstrate non-inferiority for each comparison, with a non-inferiority margin of 10 percentage points, assuming a recovery rate in the control of 77% (Table 4). For relapse outcomes, sample size will be smaller, and thus power will be lower, because only recovered children will be included in the analysis. All calculations assume a one-sided $\alpha = 0.05$ for non-inferiority and two-sided $\alpha = 0.05$ for superiority analyses.

Table 4. Sample size calculations

Scenarios with at least 80% power are **bolded**.

Primary outcome	Analysis type	Sample size per arm	Outcome prevalences reported in literature	Non-inferiority margin or detectable effect size	Assumption on control group outcome prevalence/means in sample size calculations	Power per comparison
Anthropometric recovery at discharge	Non-inferiority	360 MAM and 360 SAM children/arm enrolled; 306 MAM and 306 SAM children in analysis after 15% attrition	MAM recovery (with RUSF*): 73% (13); 73% (14); 85% (15) SAM recovery : 55.4% (16); 82.3% (17); 76% (18); 71% (pooled estimate from meta-analysis) (19)	10 percentage points (absolute difference)	55.4% (vs 45.4%)	85.6%
					77.0% (vs 67.0%)	90.0%
					82.3% (vs 72.3%)	96.8%
Relapse to wasting within 3-months post-discharge	Superiority	236 children/arm in analysis (assuming 77% of the 306 children recover)	Post-MAM relapse : 30% within 3 months (period prevalence) (20); 33% within 12-months (21) Post-SAM relapse : 6.8% 3-month cumulative incidence (22); 24% 2-month cumulative incidence (23); 30% within 3-months (unpublished); 2.6 episodes per child-year (unpublished); 1.3	35% relative reduction (incidence rate ratio = 0.65)	Incidence of 2.6 episodes per child-year	80.0%
					Prevalence of 30% (vs 20%)	71.0%

			episodes per child-year (unpublished)			
--	--	--	--	--	--	--

*RUSF = ready-to-use supplementary food

Study procedures

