## Study outcomes

### Main trial

The primary and secondary outcomes for the main trial and their definitions are listed in Table 1. Outcomes are the same for MAM and SAM children.

*Table 1. Primary and secondary efficacy outcomes*

Outcomes	Definition	Type of analysis
Primary outcomes		
Anthropometric recovery at discharge	WLZ $\geq$ -2 and MUAC $\geq$ 125 mm and absence of bilateral pitting edema for two consecutive visits, at the day of end of treatment	Non-inferiority
Relapse to wasting within 3 months post-discharge	A new episode of wasting (defined as WLZ/WHZ $<$ -2 or MUAC $<$ 125 mm or presence of bilateral pitting edema) within the 3-month period following recovery from the index wasting episode, among children who recovered from their index episode	Superiority
Length of stay (LOS) among recovered children	The number of days between the day the child is admitted to treatment and the day the child is determined to be recovered and thus discharged from treatment	Non-inferiority
Weight gain	Change in child's weight (gram/kilogram/day) between weight on day of admission to treatment and the day of end of treatment	Non-inferiority
Anthropometry at discharge from treatment	WLZ/WHZ, MUAC, weight, height/length, LAZ/HAZ and WAZ at the day of end of treatment	Non-inferiority
Anthropometry at 3-months post-discharge	WLZ/WHZ, MUAC, weight, height/length, LAZ/HAZ and WAZ at 3-months post-discharge (3 months after the day of end of treatment)	Superiority
Hemoglobin at discharge	Hemoglobin concentration (grams/liter) at the day of end of treatment	Non-inferiority
Hemoglobin at 3-months post-discharge	Hemoglobin concentration (grams/liter) at 3-months post-discharge (3 months after the day of end of treatment)	Superiority
Secondary outcomes		
Default from treatment	Child is absent for two consecutive visits, declared a defaulter on the second visit	Non-inferiority

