### Sample size and statistical power

#### Main trial

We estimate a total sample size of 1080 children with SAM (360 per arm) and 1080 children with MAM (360 per arm) will provide sufficient statistical power to demonstrate non-inferiority for each comparison, with a non-inferiority margin of relative 12.5%, assuming a recovery rate in the control of 76% and a loss to follow up of 15% (Table 4). The sample size will be smaller for analyses of relapse, because only recovered children will be included in the analysis. All calculations assume a one-sided  $\alpha = 0.05$  for non-inferiority and two-sided  $\alpha = 0.05$  for superiority analyses,  $\beta = 0.8$ , and 15% attrition. While the key objectives of this research are to evaluate effects of the alternative RUTFs on recovery and relapse, we consider as primary outcomes any outcome for which we have adequate power for clinically or policy meaningful effect sizes (5).

 Stata commands `ssi` for continuous outcomes and `artbin` for binary outcomes were used for non-inferiority analyses, and `power twomeans` for continuous outcomes and `power twoproportions` for binary outcomes were used for superiority analyses. Outcome proportions, means, or standard deviations were taken from relevant studies in literature as delineated in Table 4.

Table 4. Calculations of detectable effect sizes for all outcomes

Outcome	Outcome prevalence in the literature	Type of analysis	Non-inferiority margin (relative) with $\geq 80\%$ power (Non-inferiority)	Detectable effect size at 80% power (Superiority)	Rank of outcome
Anthropometric recovery at discharge	MAM recovery (with RUSF*): 73% (6); 73% (7); 85% (8)  SAM recovery: 55.4% (9); 82.3% (10); 76% (11); 71% (pooled estimate from meta-analysis) (12)	Non-inferiority	12.5% relative margin		Primary
Relapse to wasting within 3-months post-discharge	Post-MAM relapse: 30% within 3 months (13); 33% within 12-months (14)  Post-SAM relapse: 6.8% 3-month cumulative incidence (15); 24% 2-month cumulative incidence (16); 30% within 3-months (unpublished)	Superiority		Risk difference of 11%; Relative risk = 0.72	Primary
Length of stay (LOS) among recovered children	MAM: 36.4 days (SD 50.4 days)(17); 5.9 weeks (95% CI: 4.9, 7.0)(18) SAM: 56 days (assumed 41 day SD) (9)	Non-inferiority	MAM: 4.9 days; 12.5% relative margin SAM: 8 days; 12.5% relative margin		Primary

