Weight gain during treatment	MAM: 4.1 g/kg/day (SD = 3.0) (17), SAM: 3 g/kg/day (SD = 4.7) in 6-23 mo and 8.6 g/kg/day (SD = 4.7) in 24-59 mo (19)	Non-inferiority	MAM: 0.14 kg; 12.5% relative margin SAM: 0.91 g/kg/day; 12.5% relative margin		Primary
Anthropometry at discharge from treatment	MAM: All estimates from Fabiansen et al (20) WLZ: -1.52	Non-inferiority	MAM:		Primary

	
MUAC: 130.1 mm HAZ: -1.86 WAZ: -2.6 (assumed from SAM because estimates not available) Weight: 7.8 kg Height: 72.9 cm
 
SAM: All estimates from Kangas et al(9) WLZ: -1.9 MUAC: 125.9 mm HAZ: -2.3 WAZ: -2.6 Weight: 7.3 kg Height: 71.6 cm
		
WLZ: 0.2 z-scores; 12.5% relative margin MUAC: 6.8 mm; 5% relative margin HAZ: 0.2 z-scores; 12.5% relative margin WAZ: 0.4 z-scores; 12.5% relative margin Weight: 0.4 kg; 5% relative margin Height: 3.8 cm; 5% relative margin
 
SAM: WLZ: 0.3 z-scores; 12.5% relative margin MUAC: 6.3 mm; 5% relative margin HAZ: 0.3 z-scores; 12.5% relative margin WAZ: 0.4 z-scores; 12.5% relative margin Weight: 0.4 kg; 5% relative margin Height: 3.8 cm; 5% relative margin
		
Anthropometry at 3-months post-discharge	MAM: All estimates from Fabiansen et al (20)	Superiority		MAM: WLZ: 0.26	Primary

	WLZ: -1.52 MUAC: 130.1 cm HAZ: -1.86 WAZ: -2.6 (assumed from SAM because estimates not available) Weight: 7.8 kg Height: 72.9 cm  SAM: All estimates from Kangas et al(9) WLZ: -1.9 MUAC: 125.9 cm HAZ: -2.3 WAZ: -2.6 Weight: 7.3 kg Height: 71.6 cm			MUAC: 2.46 cm HAZ: 0.39 WAZ: 0.37 Weight: 0.39 kg Height: 1.87 cm  SAM: WLZ: 0.37 MUAC: 3.13 cm HAZ: 0.48 WAZ: 0.37 Weight: 0.55 kg Height: 2.76 cm	
Hemoglobin at discharge	MAM: 108 g/L (SD = 13) (21) SAM: 108.6 g/L (SD = 11.2) (22)	Non-inferiority	MAM: 2.7 g/L; 2.5% relative margin SAM: 2.2 g/L; 2.5% relative margin		Primary
Hemoglobin at 3-months post-discharge	MAM: 108.0 g/L (SD = 13) (21) SAM: 108.6 g/L (SD = 11.2) (22)	Superiority	--	MAM = 2.9 g/L SAM = 2.9 g/L	Primary
Default from treatment	MAM: 6.8% (17) SAM: 8.5% (9)	Non-inferiority	MAM: 50% relative margin SAM: 45% relative margin		Secondary
Transfer to inpatient treatment	MAM: 5.8% (20) SAM: 20.1% (9)	Non-inferiority	MAM: 70% relative margin SAM: 40% relative margin		Secondary
Non-response to treatment	MAM: 32.2% (18), 28%(20) SAM: 12.5% (9)	Non-inferiority	MAM: 30% relative margin SAM: 25% relative margin		Secondary

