### Sub-group and sensitivity analyses

We will conduct two *a priori* sub-group analyses for primary study outcomes only. These are for exploratory purposes, and our study did not factor these sub-groups into account in power calculations. We will assess all primary study outcomes separately among the following sub-groups of children:

1. Age group at enrollment: 6-23 months vs 24-59 months
2. Children with high-risk MAM, defined as MAM status at enrollment (defined as above) and any of the following characteristics:
  - a. Age 6-23 months
  - b. WAZ < -3
  - c. MUAC 115-119 mm
  - d. History of SAM
  - e. Present case of MAM is a relapse case

We hypothesize the alternative RUTFs may have a different effect in these sub-groups. First, if the alternative RUTFs impact the gut microbiome of children, these interventions may have greater impact on the anthropometry outcomes of younger children. The gut microbiome before three years of age is especially sensitive to external influences such as nutrition, and thus may represent a critical window in which interventions may have the most influence (32). Conversely, one study on a previous formula of SMS-RUTF reported lower efficacy among children 6-23 months of age (33), although a subsequent study reported non-inferiority of the SMS-RUTF product among this age group after it had been reformulated (19). Further data on the efficacy of this product within the subgroup of 6–23-month-old children is useful.

Children with MAM or SAM have microbiome profiles that are more immature for their age and this deleterious microbiome immaturity is inversely associated with WHZ even within MAM or SAM categories (34). Thus, we hypothesize that children with high-risk MAM may have gut microbiome profiles that are more suboptimal than their lower-risk MAM counterparts, and thus may stand to experience a stronger benefit from any microbiome influences exerted by the products. Additionally, release of new WHO guidelines on the prevention and management of wasting in 2023 recommend prioritize specialized food products (such as RUTF) for high-risk MAM (35), and thus efficacy data within this sub-group may be useful for policymakers in Burkina Faso in implementing these guidelines in the coming years.

As described above, we will conduct one sensitivity analysis, in which we exclude children whose treatment product was switched to the standard RUTF before the expiration date of their treatment product.

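### SAP Table 4 gives no consistent margin for weight gain, a primary outcome: the MAM margin is in kilograms, the SAM margin is not 12.5% of either listed mean, and the stated 80% power is not reached after attrition

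*SAP*

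**What the plan says.** - **Outcome.** SAP Table 1 lists weight gain under primary outcomes, defined as "Change in child's weight (gram/kilogram/day) between weight on day of admission to treatment and the day of end of treatment".
- **Planning values.** SAP Table 4 gives "MAM: 4.1 g/kg/day (SD = 3.0) (17), SAM: 3 g/kg/day (SD = 4.7) in 6-23 mo and 8.6 g/kg/day (SD = 4.7) in 24-59 mo".
- **Margins.** The same row prints "MAM: 0.14 kg; 12.5% relative margin SAM: 0.91 g/kg/day; 12.5% relative margin". The column is headed "Non-inferiority margin (relative) with $\geq 80\%$ power".
- **Length of stay (LOS).** SAP Table 4 prints "MAM: 4.9 days; 12.5% relative margin SAM: 8 days; 12.5% relative margin". The row's means are 36.4 days (SD 50.4) and 5.9 weeks for MAM, and 56 days (assumed SD 41) for SAM.
- **Sample size.** Both documents plan 360 per arm in each stratum, 15% attrition and one-sided alpha 0.05 for non-inferiority. Protocol Table 4 puts 306 per arm in the analysis, and 236 per arm among recovered children.
- **Primary rank.** The SAP's sample size section ranks an outcome as primary when power is adequate for a meaningful effect.
- **Analysis.** SAP Statistical methods compares continuous outcomes as between-arm differences from linear regression, separately for MAM and SAM. The 12.5% decision rule there is written for the relative risk. No rule is given for a continuous outcome, and the text does not say whether the absolute or the percentage form of a Table 4 margin governs.

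**The concern.** A non-inferiority conclusion is only as good as its margin. For weight gain the SAP prints two forms of the margin in each stratum, and they do not agree. In MAM they are not even in the same unit as the outcome. In SAM the absolute form matches the percentage form only under an age mix that the SAP never states. With no decision rule for continuous outcomes, the analyst would have to choose between forms that could give different answers on a primary outcome.

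Power matters too. The SAP uses adequate power as its reason for ranking outcomes as primary. If the printed margins do not carry 80% power at the planned analysed sample, that reason fails for this outcome.

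**Working it through.** **1. Do the margins equal 12.5% of the listed means?**

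| Stratum | Listed mean (g/kg/day) | 12.5% of mean | Printed margin | Printed / mean |
|---|---|---|---|---|
| MAM | 4.1 | 0.5125 | 0.14 kg | different unit |
| SAM, 6-23 mo | 3.0 | 0.375 | 0.91 | 30.3% |
| SAM, 24-59 mo | 8.6 | 1.075 | 0.91 | 10.6% |

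*MAM.* Read as g/kg/day, 0.14 would be 0.14/4.1 = 3.4%, so it is not a mislabelled 12.5%. As kilograms it is 12.5% of 0.14/0.125 = 1.12 kg total gain. Assuming a 36.4-day stay and a child of 7.3 to 7.8 kg, 0.125 × 4.1 × weight × 36.4/1000 gives 0.136 to 0.146 kg. So 0.14 kg may be a total-gain margin, but the SAP shows no such conversion.

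*SAM.* 0.91/0.125 = 7.28. The share aged 24-59 months needed for that mean is (7.28 − 3.0)/(8.6 − 3.0) = 0.76. No mix is stated. If 50% to 90% of SAM children were 6-23 months (an assumption), the pooled mean would be 5.80 to 3.56, and 0.91 would be 15.7% to 25.6% of it.

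**2. Length of stay**

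- MAM: 5.9 weeks = 41.3 days; (36.4 + 41.3)/2 = 38.85; 12.5% of this is 4.86, which rounds to the printed 4.9. It reproduces.
- SAM: 12.5% of 56 = 7.0 days. The printed 8 days is 8/56 = 14.3%. It does not reproduce.

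**3. Power**

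Formula: power = Φ( margin / (SD × √(2/n)) − 1.645 ), with true difference 0 and one-sided alpha 0.05. n = 360 × 0.85 = 306 per arm.

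| Outcome and margin | SD | n = 306 | Other n |
|---|---|---|---|
| MAM weight gain, 0.5125 | 3.0 | Φ(2.113 − 1.645) = 68% | 74% at 360 |
| SAM weight gain, 0.91 | 4.7 | Φ(2.395 − 1.645) = 77% | 83% at 360 |
| MAM LOS, 4.9 days | 50.4 | Φ(1.203 − 1.645) = 33% | 28% at 236 |
| SAM LOS, 8 days | 41 | Φ(2.414 − 1.645) = 78% | 68% at 236 |

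LOS is defined among recovered children, so the 236 column is the closer one for it.

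Sample size for 80% power, n = 2 × (1.645 + 0.842)² × SD² / margin²:

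- MAM at 0.5125: 424 analysed per arm; 424/0.85 gives 499 enrolled.
- SAM at 0.91: 330 analysed per arm; 330/0.85 gives 389 enrolled.

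The plan has 360 enrolled. At 306 per arm, the MAM margin that does carry 80% power is 3.0 × √(2/306) × 2.486 = 0.60 g/kg/day, or 14.7% of 4.1.

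**4. SAM at a true 12.5% of a pooled mean** (assumed mixes, SD 4.7, n = 306)

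- 50% aged 6-23 months: margin 0.725, power 60%.
- 90% aged 6-23 months: margin 0.445, power Φ(1.171 − 1.645) = 32%.

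The SD of 4.7 is listed within each age group. Pooling groups whose means differ by 5.6 raises it to √(4.7² + w(1 − w) × 5.6²), where w is the share aged 6-23 months. At w = 0.236, the mix that makes 0.91 equal 12.5%, the SD is 5.27 and power at 0.91 is 69%. The 77% above is therefore on the favourable side unless age is in the model.

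**The case against.** The best defence is that the column heading describes its margins as relative, so 12.5% is the margin and the absolute figures are illustrations. That is plausible, but the SAP does not say so for continuous outcomes, and its regression yields an absolute difference. The SAM power shortfall at 0.91 (77% against 80%) is also small. The MAM shortfall is not.

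Several stronger readings are tempting, and the documents do not support them:

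- **That the weight-gain threshold cannot be applied at all.** The SAM figure is in the outcome's own unit and can be compared with a regression difference. In MAM only the kilogram form is unusable. The accurate statement is that the margin is not uniquely defined.
- **That the plan tolerates 30% slower gain in young SAM children.** The main analysis pools SAM ages. The 30.3% would arise only if 0.91 were carried into the exploratory 6-23 month subgroup, for which no margin is stated, or if nearly all SAM children were that young.
- **That the SAP signals a known problem in that age group.** It says one study of an earlier formulation "reported lower efficacy among children 6-23 months of age", but the same sentence adds that a later study found the reformulated product non-inferior there.
- **That a slower product given for longer would pass.** No test of total kilograms is planned; Table 1 defines a rate.
- **That both LOS margins are wrong.** The MAM 4.9 days follows from averaging the row's two means, although the SAP does not show the step. It should stay.

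**Conclusion.** The point holds as an inconsistency in margins and power. The MAM weight-gain margin is in the wrong unit for the outcome. The SAM margin of 0.91 is not 12.5% of either listed mean and depends on an unstated age mix. The SAM LOS margin is one day wider than its label (14.3%, not 12.5%).

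At the planned 306 per arm the 80% heading is not met for weight gain: about 68% for MAM at 0.51 g/kg/day, and 77% for SAM at 0.91 (83% only if attrition is ignored). LOS at its printed margins has about 33% (MAM) and 78% (SAM), and less among recovered children.

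These figures assume a true difference of zero, the SAP's own SDs, 15% attrition and one-sided alpha 0.05. The MAM LOS figure rests on the single listed SD of 50.4 days. Results for assumed SAM age mixes show a range only, because the documents give no mix.

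**What to change.** In a dated SAP amendment before unblinding:

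1. State one weight-gain margin per stratum in g/kg/day. MAM: 12.5% of 4.1 = 0.51. SAM: 12.5% of an age-weighted mean that the SAP states, with its SD and age mix.
2. Delete the 0.14 kg figure and the unexplained 0.91.
3. Say that this margin governs the between-arm difference from the regression, and write the decision rule for continuous outcomes.
4. For LOS, set the SAM margin to 7.0 days or restate its percentage as 14.3%. Leave MAM at 4.9 days and show that it comes from the average of the two cited means.
5. Print the recomputed power beside each margin at the analysed sample size, using recovered children for LOS. Where it falls below 80%, say on what basis the outcome keeps its primary rank.

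The cost is a text change with no new data. Stated power becomes less favourable. For SAM LOS at 7.0 days it is Φ(2.112 − 1.645) = 68% at 306 per arm. The SAP describes late-enrolment product switching in the past tense, so the margins would be changed after enrolment. The amendment therefore needs a dated justification showing that treatment codes had not been released.

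### SAP Table 4 states each continuous non-inferiority margin twice, and five of the 18 pairs disagree beyond rounding (four wider, one stricter), with no rule on which figure governs

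*SAP*

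**What the plan says.** SAP Table 1 ranks length of stay, weight gain, anthropometry at discharge and hemoglobin at discharge as primary outcomes tested for non-inferiority. SAP Table 4 gives their margins in a column headed "Non-inferiority margin (relative) with" at least 80% power. Each cell holds an absolute value and a percentage, and a neighbouring column gives the literature mean. Examples are "SAM: 8 days; 12.5% relative margin", "WAZ: 0.4 z-scores; 12.5% relative margin" (both strata), "WLZ: 0.3 z-scores; 12.5% relative margin" (SAM), "MUAC: 6.8 mm; 5% relative margin" (MAM) and "Height: 3.8 cm; 5% relative margin" (both strata).

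The SAP section on sample size for the main trial sets one-sided α = 0.05 for non-inferiority, 15% attrition and "1080 children with SAM (360 per arm"), with the same number of MAM children. It also says that an outcome counts as primary where power is adequate for a meaningful effect.

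The SAP section Statistical methods states a non-inferiority rule only for the relative risk of binary outcomes. For continuous outcomes it says that linear regression will estimate differences between arms, and it names no margin and no rule.

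**The concern.** If the two figures in a cell were the same margin in two units, either could be used. Where they differ, a confidence bound can fall between them. For SAM length of stay, an upper bound of 7.5 days is non-inferior against 8 days and not against 7.0. Because the Statistical methods section is silent on continuous outcomes, Table 4 is the only place a reader can find a margin, and the choice between the figures could be made after the data are seen. The choice also changes power, and the SAP makes power the criterion for ranking an outcome as primary.

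**Working it through.** **Inputs.** Means, SDs and margins come from SAP Table 4. The number per arm is 360 × 0.85 = 306. The number recovered per arm is 236, from Protocol Table 4 (77% of 306).

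**Step 1: convert each percentage.** Absolute margin = m × |mean|, compared with the printed value within its own rounding. The last column tests a second conversion, |mean| × m/(1 − m).

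| Outcome | m × mean | Printed | m/(1 − m) × mean |
|---|---|---|---|
| SAM length of stay | 0.125 × 56 = 7.0 d | 8 | 8.0 |
| WAZ, MAM and SAM | 0.125 × 2.6 = 0.325 | 0.4 | 0.371 |
| SAM WLZ | 0.125 × 1.9 = 0.2375 | 0.3 | 0.271 |
| SAM hemoglobin | 0.025 × 108.6 = 2.715 g/L | 2.2 | 2.785 |
| MAM MUAC | 0.05 × 130.1 = 6.505 mm | 6.8 | 6.847 |
| MAM height | 0.05 × 72.9 = 3.645 cm | 3.8 | 3.837 |
| SAM height | 0.05 × 71.6 = 3.58 cm | 3.8 | 3.768 |
| SAM MUAC | 0.05 × 125.9 = 6.295 mm | 6.3 | 6.626 |
| MAM HAZ | 0.125 × 1.86 = 0.2325 | 0.2 | 0.266 |
| MAM hemoglobin | 0.025 × 108 = 2.7 g/L | 2.7 | 2.769 |

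**Step 2: allow for rounding of the printed absolute value.**
- WAZ: 0.4 covers 0.35 to 0.45, so the excess over 0.325 is 8% to 38%.
- SAM WLZ: 0.3 covers 0.25 to 0.35, so the excess over 0.2375 is 5% to 47%.
- SAM length of stay: 8/7.0 = 1.14. If 8 is a whole-day rounding, the smallest value is 7.5, still 7% above 7.0.
- SAM hemoglobin: 2.2/2.715 = 0.81, about 19% stricter. The printed value implies 2.2/108.6 = 2.0%.
- MAM MUAC and both heights imply 5.2%, 5.2% and 5.3%, which would print as 5% if the percentage was rounded.

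**Step 3: account for all 18 pairs.**
- Five clearly disagree: SAM length of stay, WAZ twice, SAM WLZ and SAM hemoglobin.
- Three differ slightly: MAM MUAC and height twice.
- Seven agree: WLZ, HAZ, weight and hemoglobin in MAM; MUAC, HAZ and weight in SAM.
- Two depend on the base. MAM length of stay is printed as 4.9 days. The two cited means give 0.125 × 36.4 = 4.55 and 0.125 × 41.3 = 5.16, and their average gives 4.86. SAM weight gain is printed as 0.91, against 0.375 for the younger group, 1.075 for the older group and 0.725 for their simple average.
- One cannot be compared: MAM weight gain is printed as 0.14 kg, while 12.5% of 4.1 is 0.51 g/kg/day.

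**Step 4: look for one convention.** The m/(1 − m) form reproduces every wide row, but it fails for SAM MUAC, MAM HAZ and both hemoglobin rows. Neither conversion fits the whole column.

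**Step 5: power.** Power = Φ(margin / (SD × √(2/n)) − 1.645), with true difference 0. For SAM length of stay, SD = 41:
- n = 306, standard error 3.31: 8 days gives 77.9%, 7 days gives 68.0%.
- n = 236, standard error 3.77: 8 days gives 68.3%, 7 days gives 58.3%.

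The margin that reaches 80% is 8.24 days at n = 306 and 9.39 days at n = 236. For SAM hemoglobin (SD 11.2, n = 306), 2.2 gives 78.4% and 2.7 gives 91.2%.

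Table 4 prints no SDs for discharge anthropometry. As an assumption, the SD can be back-solved from the 3-month superiority effect of 0.37 (WAZ in both strata, SAM WLZ): SD = 0.37 / (2.80 × √(2/n)), which is 1.63 if that calculation used n = 306 and 1.43 if it used 236. With 306 per arm at discharge, WAZ power is then 92% to 96% at 0.4 and 79% to 88% at 0.325. SAM WLZ power is 73% to 83% at 0.3 and 56% to 66% at 0.2375.

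**The case against.** Table 4 is titled as a table of detectable effects, so calling its entries decision thresholds is an inference. That is fair, but neither document contains another continuous margin, and a non-inferiority test cannot be run without one.

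The wide rows may come from a different base and not from slips: m/(1 − m) gives SAM length of stay as exactly 8.0. This is a plausible explanation. It does not resolve the matter, because the SAP does not state it and four rows contradict it. For the same reason the products in Step 1 cannot be called the correct margins.

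A reader might infer that the mismatches all make non-inferiority easier. The documents do not support that: SAM hemoglobin errs the strict way, and seven pairs agree. A reader might also take MAM MUAC and height as clear errors. Their gaps are 0.3 mm and about 0.2 cm, and on SDs back-solved as above (MUAC effect read as mm) power is about 98% to 100% under either figure.

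On power, 8.24 days would itself print as 8, so the shortfall at 306 per arm under the wider margin is within rounding. That defence does not cover the 7-day margin. Nor does it cover the recovered children, who are the population defined for this outcome.

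**Conclusion.** The inconsistency is real but limited. Five of 18 pairs conflict beyond rounding. Four absolute margins are wider than their percentage of the printed mean: SAM length of stay by 14% as printed, WAZ in both strata by at least 8% and SAM WLZ by at least 5%. SAM hemoglobin is about 19% stricter. The MAM weight-gain margin is in the wrong unit for its outcome. No single conversion explains the column, and nothing says which figure governs.

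As printed, SAM length of stay does not reach the column's 80% under either margin. The gap is marginal at 8 days with 306 per arm and clear otherwise. This rests on the SAP's assumed SD of 41 days, no true difference, and the Protocol's 77% recovery for the 236.

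The documents do not show that margins were loosened on purpose. The binary recovery margin is not affected by this point.

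**What to change.** Before unblinding, amend the SAP as follows.
- In Table 4, name one reference mean and one conversion. Give a single governing margin per outcome and stratum, in absolute units so that it matches the regression difference.
- Correct every discordant row. Include SAM hemoglobin, where applying the stated percentage would loosen the margin, and the MAM weight-gain unit. State the base for MAM length of stay and SAM weight gain.
- In Statistical methods, add the non-inferiority rule for continuous outcomes: which confidence bound is compared with which margin, and in which direction harm lies for each outcome.
- Restate power row by row, using recovered children for length of stay, and check it against the 80% heading and the primary ranking.

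The SAP withholds the product codes until analyses are complete, so this can be done blind. The cost is SAP wording, less favourable stated power, and possibly a change of rank for SAM length of stay.

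### SAP Table 4 gives the SAM non-inferiority margin for hemoglobin at discharge as two different values: 2.2 g/L and 2.5% (2.7 g/L)

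*SAP*

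**What the plan says.** SAP Table 1 ranks hemoglobin at discharge (non-inferiority) and hemoglobin at 3 months post-discharge (superiority) as primary outcomes. Protocol Table 3 lists both as secondary.

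SAP Table 4 gives, for hemoglobin:

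- Base values: MAM mean 108 g/L, SD 13; "SAM: 108.6 g/L (SD = 11.2) (22").
- Margin at discharge: 2.7 g/L and 2.5% for MAM; for SAM, "SAM: 2.2 g/L; 2.5% relative margin". The column is headed "Non-inferiority margin (relative) with $\geq 80\%$ power (Non-inferiority").
- Effect at 3 months: "MAM = 2.9 g/L SAM = 2.9 g/L", in the column headed "Detectable effect size at 80% power (Superiority").

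The SAP's sample size section plans "1080 children with SAM (360 per arm) and 1080 children with MAM (360 per arm") and assumes 15% attrition throughout. It says that the sample will be smaller for relapse analyses, which are limited to recovered children. Protocol Table 4 prints the resulting numbers: 306 per arm after attrition, and 236 per arm for relapse if 77% recover. On error rates the protocol states: "All calculations assume a one-sided $\alpha = 0.05$ for non-inferiority and two-sided $\alpha = 0.05$ for superiority analyses". The SAP gives the same values.

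**The concern.** A relative margin applied to a stated mean fixes the absolute margin. In the MAM line the two forms agree; in the SAM line they do not. Because non-inferiority is read by comparing a confidence limit with the margin, two margins for one primary outcome leave part of the result range without a defined verdict. The SAP also ranks an outcome as primary when power is adequate for a meaningful effect, so the power attached to this margin bears on the outcome's rank.

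The 3-month row raises a smaller question. The two strata have different SDs and the same planned size, yet show the same detectable effect.

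**Working it through.** **Inputs.** Means 108 and 108.6 g/L, and SDs 13 (MAM) and 11.2 (SAM), from SAP Table 4. Analysed n = 360 x 0.85 = 306 per arm. One-sided alpha 0.05 for non-inferiority (z = 1.645); two-sided 0.05 for superiority (z = 1.960); 80% power (z = 0.842). True difference zero for non-inferiority. Normal approximation.

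**Step 1: reproduce the MAM line.** 0.025 x 108 = 2.70 g/L, as printed. SE = 13 x sqrt(2/306) = 1.051. Power = Phi(2.70/1.051 - 1.645) = 82%, which satisfies the column heading.

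**Step 2: the SAM line.** 0.025 x 108.6 = 2.715 g/L, not 2.2. Conversely, 2.2/108.6 = 2.03%. The gap is about 0.5 g/L.

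Some rows of Table 4 seem to convert by mean/(1 - r) - mean; SAM length of stay, 56/0.875 - 56 = 8 days, is one. That convention gives 108.6/0.975 - 108.6 = 2.78 g/L, further from 2.2. A 2.0% margin gives 2.17 or 2.22 g/L under the two conventions, and both round to 2.2. So 2.2 g/L and 2.5% are different margins either way.

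**Step 3: power in SAM at 306 per arm.** SE = 11.2 x sqrt(2/306) = 0.905.

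| Margin | Share of 108.6 | Power |
|---|---|---|
| 2.2 g/L | 2.0% | Phi(2.2/0.905 - 1.645) = 78.4% |
| 2.715 g/L | 2.5% | Phi(2.715/0.905 - 1.645) = 91.2% |

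The margin with exactly 80% power is (1.645 + 0.842) x 0.905 = 2.25 g/L. The printed 2.2 is close to it and may have been derived from power, but the SAP does not say so. Exactly 80% at 2.2 g/L needs 321 per arm analysed, or 321/0.85 = 378 enrolled.

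**Step 4: size of the ambiguous zone.** The lower limit is the observed difference minus 1.645 x 0.905 = 1.49 g/L. Observed differences (intervention minus control) between about -1.2 and -0.7 g/L would pass at 2.7 and fail at 2.2. If the products are truly equal, the chance of landing there is 91.2% - 78.4% = about 13% for each comparison.

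**Step 5: superiority at 3 months.** Detectable effect = (1.960 + 0.842) x SD x sqrt(2/n).

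| n per arm | MAM (SD 13) | SAM (SD 11.2) |
|---|---|---|
| 306 | 2.94 g/L | 2.54 g/L |
| 236 | 3.35 g/L | 2.89 g/L |

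At equal n the effects differ by 13/11.2 = 1.16. Allowing 2.9 to stand for 2.85 to 2.95, MAM needs about 305 to 327 per arm and SAM about 227 to 243. The ranges do not overlap, so no common n gives both figures.

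The row for anemia at 3 months shows a similar pattern. It prints 23.3% for MAM and 24.2% for SAM, which imply about 295 and 254 per arm; at 306 they would be 22.9% and 22.1%.

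**The case against.** **The table already points to the answer.** The column is headed as a relative margin with at least 80% power, and only 2.5% satisfies it. This stands as a reason to think 2.5% was meant. It does not remove the 2.2 g/L, which is the only figure in the cell on the scale of the planned linear regression.

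**2.2 g/L could have adequate power.** At 360 per arm it has 83.9%. But the SAP says its calculations assume 15% attrition. At 306, any value that rounds to 2.2 (2.15 to 2.25) has between 76.7% and just under 80.0%. The shortfall is small.

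**Table 4 may not be the decision source.** It is titled as a table of detectable effect sizes, and the SAP's Statistical methods section gives a 12.5% margin only for binary outcomes, with no non-inferiority rule for continuous ones. This is correct, and it means that fixing the cell alone is not enough: the SAP must also say that the figure decides the outcome.

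**The superiority row.** A reader might infer that MAM was computed on all children (306) and SAM on recovered children only (236). The documents do not support that as a fact. No n is printed for the row, the matches are ranges, and a value copied from the MAM entry to the SAM entry would look the same. The SAP limits the smaller sample to relapse, and Table 1 does not restrict hemoglobin at 3 months to recovered children. So 306 is the documented n and the SAM figure is the likelier slip. It is conservative: at 306 per arm, 2.9 g/L in SAM has about 89% power.

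**Conclusion.** The SAM margin for hemoglobin at discharge is inconsistent as written: 2.2 g/L is 2.0% of the stated mean, and 2.5% is 2.7 g/L. Power is about 78% and 91% respectively, and only the second meets the column heading. These power figures rest on 306 analysed per arm, SD 11.2, no true difference and one-sided alpha 0.05. The mismatch itself needs only the printed mean. It matters because no other statement in the documents fixes a hemoglobin margin.

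The 3-month figures of 2.9 g/L in both strata cannot both hold at one n. At 306 per arm they are about 2.9 (MAM) and 2.5 (SAM) g/L; at 236, about 3.4 and 2.9. This is a reporting correction, since a detectable effect is not a decision threshold.

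A reader might go further and conclude that the trial is underpowered for hemoglobin. The documents do not support that: at the 2.5% margin, power exceeds 80% in both strata. The SAP also names recovery and relapse as the key objectives, and this point does not affect them.

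**What to change.** Before unblinding, amend SAP Table 4 and the Statistical methods section:

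1. Give one SAM margin for hemoglobin at discharge, in g/L, with its matching percentage and power, and state that it is the decision margin for this outcome.
   - If 2.5% is kept, print 2.7 g/L (power about 91%).
   - If 2.2 g/L is kept, print 2.0% with about 78% power, and acknowledge that it falls short of the 80% in the column heading and that the outcome's primary rank rests on adequate power.
2. For hemoglobin at 3 months, state the n per arm and the analysis set for each stratum and recompute both effects on that basis. Check the anemia row at 3 months in the same way.

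The cost is SAP wording and a short recalculation. Enrolment and data collection do not change. Settling the margin while allocation is still concealed also prevents it from appearing chosen to suit the result.
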